- Reoperations (date, duration, post-operative x-ray, need of blood transfusion, intraoperative fluoroscopy and measures and main reasons of reoperation) performed within the 12 months after nail implant.
- ADEs/SADEs reported since the day of surgery until the last follow-up visit.
- MDDs reported since the day of surgery until the last follow-up visit.
- Concomitant medication prescribed since surgery until the last follow-up visit.

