18 DISCHARGE VISIT

This analysis will be performed on FAS population.

The descriptive statistic (Mean, SD, Median, Q₁, Q₃, Min, Max) will be shown for the following continuous variable:

- Time from surgery to Discharge (days) (calculated as Date of discharge minus date of surgery)

The categorical variable to be described is, N and (%):

- Time from surgery to Discharge (days) within the time windows estimated in the protocol (1-20 days)? (Yes / No)

The categorical variable to be described is, N and (%):

- Was any medication prescribed to the patient due to the surgery? YES / NO, If “YES” will be described:
 - Antibiotic
 - Anti-inflammatory
 - Analgesic
 - Heparin
 - Other (A list will be shown)
- Did the patient refer any info related to pain at the site of nail application? YES / Data not available), If “YES” will be described:
 - No pain
 - Pain

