19 FIRST FOLLOW UP VISIT (1 MONTH)

This analysis will be performed on FAS population.

The descriptive statistic (Mean, SD, Median, Q₁, Q₃, Min, Max) will be shown for the following continuous variable:

- Time from surgery to first follow up visit (months) (calculated as Date of first follow up minus date of surgery)

The categorical variable to be described is, N and (%):

- Time from surgery to first follow up visit (months) within the time windows estimated in the protocol (1-3 months)? (Yes / No)

The categorical variables to be described are, N and (%):

- Was the patient examined on an outpatient basis or contacted by telephone because he was unable to reach your hospital? (Outpatient visit / Telephone contact)
- Have the medications the patient takes regularly changed? YES / NO, If "YES", type and dosage will be shown.
- Did the patient refer any info related to pain at the site of nail application? YES / Data not available), If "YES" will be described:
 - No pain
 - Pain
- Are follow up fluoroscopies (AP + ML) or, preferably, RX (AP + ML) available? YES / NO

The descriptive statistic (Mean, SD, Median, Q₁, Q₃, Min, Max) will be shown for the following continuous variables:

- Xap (mm)
- Dap (mm)
- Xlat (mm)
- Dlat (mm)
- TAD (mm)

The categorical variables to be described are, N and (%):

- Observer 1: According to medical opinion, is/are the fracture/s treated with Chimaera nail consolidated? YES / NO, If "NO", motivate will be described
- Observer 2: According to medical opinion, is/are the fracture/s treated with Chimaera nail consolidated? YES / NO, If "NO", motivate will be described.

- Number of patients in which consolidation has been achieved according to the two observers.

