20 SECOND FOLLOW UP VISIT (6 MONTHS)

This analysis will be performed on FAS population.

The descriptive statistic (Mean, SD, Median, Q₁, Q₃, Min, Max) will be shown for the following continuous variable:

- Time from surgery to second follow up visit (months) (calculated as Date of second follow up minus date of surgery)

The categorical variable to be described is, N and (%):

- Time from surgery to second follow up visit (months) within the time windows estimated in the protocol (3-9 months)? (Yes / No)

The categorical variables to be described are, N and (%):

- Was the patient examined on an outpatient basis or contacted by telephone because he was unable to reach your hospital? (Outpatient visit / Telephone contact)
- Have the medications the patient takes regularly changed? YES / NO, If "YES", type and dosage will be shown.
- Did the patient refer any info related to pain at the site of nail application? YES / Data not available), If "YES" will be described:
 - No pain
 - Pain

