21 THIRD FOLLOW UP VISIT (12 MONTHS)

This analysis will be performed on FAS population.

The descriptive statistic (Mean, SD, Median, Q₁, Q₃, Min, Max) will be shown for the following continuous variable:

- Time from surgery to third follow up visit (days) (calculated as Date of third follow up minus date of surgery)

The categorical variable to be described is, N and (%):

- Time from surgery to third follow up visit (months) within the time windows estimated in the protocol (9-15 months)? (Yes / No)

The categorical variables to be described are, N and (%):

- Was the patient examined on an outpatient basis or contacted by telephone because he was unable to reach your hospital? (Outpatient visit / Telephone contact)
- Have the medications the patient takes regularly changed? YES / NO, If "YES", type and dosage will be shown.
- Did the patient refer any info related to pain at the site of nail application? YES / Data not available), If "YES" will be described:
 - No pain
 - Pain
- During the year did the patient come back to work? (YES / NO / At time of surgery the patient didn't work at all / Data not available)
- Are follow up fluoroscopies (AP + ML) or, preferably, RX (AP + ML) available? YES / NO

The descriptive statistic (Mean, SD, Median, Q₁, Q₃, Min, Max) will be shown for the following continuous variables:

- Xap (mm)
- Dap (mm)
- Xlat (mm)
- Dlat (mm)
- TAD (mm)

The categorical variables to be described are, N and (%):

- Observer 1: According to medical opinion, is/are the fracture/s treated with Chimaera nail consolidated? YES / NO, If "NO", motivate will be described
- Observer 2: According to medical opinion, is/are the fracture/s treated with Chimaera nail consolidated? YES / NO, If "NO", motivate will be described.

- Number of patients in which consolidation has been achieved according to the two observers.

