24.1 ADDITIONAL SURGERY

24.1.1 ADDITIONAL SURGERY DESCRIPTION

The categorical variables to be described are, N and (%) and Clopper-Pearson confidence intervals will be shown at 95.0% as well:

- Patients with at least one additional surgery
- Number of additional surgeries per patient
- What is the reason of additional surgery? (Adverse Event / Device Deficiency / Secondary dynamization / Other (a list will be shown))
- Number of patients with at least one additional surgery which reason was Adverse Event
- Number of patients with at least one additional surgery which reason was Device Deficiency
- Number of patients with at least one additional surgery which reason was Adverse Secondary dynamization
- Number of patients with at least one additional surgery which occurs in surgery visit
- Number of patients with at least one additional surgery which occurs in discharge visit
- Number of patients with at least one additional surgery which occurs in follow up visit 1
- Number of patients with at least one additional surgery which occurs in follow up visit 2
- Number of patients with at least one additional surgery which occurs in follow up visit 3

For the total number of additional surgeries, the descriptive statistic (Mean, SD, Median, Q₁, Q₃, Min, Max) will be shown for the following continuous variable:

- Duration of the surgery (skin to skin) (minutes)

For the total number of additional surgeries, the categorical variables to be described are, N and (%):

- Has the patient been transfused? YES / NO, If "YES", descriptive statistic (Mean, SD, Median, Q₁, Q₃, Min, Max) of the number of used blood bags will be shown

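### SAP 24.1.1 times additional surgery only by visit label, so its counts mix period length with timing and cannot give the 6-month safety result

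*SAP*

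**What the plan says.** For the safety population, SAP 24.1.1 plans N, % and 95% Clopper-Pearson intervals for patients with any additional surgery. It also plans the number of surgeries per patient, the reason (adverse event, device deficiency, secondary dynamization, other) and patient counts for the first three of these reasons. Timing appears only in five further rows. They run from "Number of patients with at least one additional surgery which occurs in surgery visit" through discharge and follow-up 1 to "Number of patients with at least one additional surgery which occurs in follow up visit 2" and follow-up 3. These rows are not split by reason. No rule says which label a surgery between two visits receives, and no time from implant to additional surgery is planned, although SAP 23 does calculate time from surgery to consolidation.

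The visits are placed as follows:

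- Discharge (SAP 18): "within the time windows estimated in the protocol (1-20 days".
- Follow-up 1 (SAP 19, headed 1 month): "within the time windows estimated in the protocol (1-3 months".
- Follow-up 2 (SAP 20, headed 6 months): "within the time windows estimated in the protocol (3-9 months".
- Follow-up 3 (SAP 21, headed 12 months): "within the time windows estimated in the protocol (9-15 months".

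The secondary (safety) objective stops at 6 months after implant (Protocol 7.2, SAP 7 and 24). Protocol 13.1.2.2 defines the safety variable as reoperation caused by an ADE/SADE or MDD up to 6 months.

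Protocol 11.2 collects, for reoperations within 12 months, "Reoperations (date, duration, post-operative x-ray, need of blood transfusion" and other items. The SAP also plans a listing of additional surgeries with their characteristics, but does not itemise them.

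**The concern.** A reoperation seldom happens at a scheduled visit, so a visit label is a coarse stand-in for time since implant. The labels are also unequally spaced. A reader who sees few surgeries under discharge and follow-up 1 and more under follow-ups 2 and 3 could take this for late device trouble when it may only reflect longer periods. Because visit windows are wide, the same label can also mean quite different times since implant in two patients.

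The larger issue is the stated endpoint. The safety result is defined to 6 months, while additional surgeries are counted to follow-up 3. If no row is cut at 6 months, the plan does not specify the number that its secondary objective asks for.

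**Working it through.** The plan states no figure for the by-visit counts, so there is none to reproduce. The steps below use its own visit times.

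**Assumptions.** (a) A label covers the time since the previous visit; the SAP does not say so. (b) Discharge is at day 10; the SAP gives only 1-20 days. (c) A month is about 30.4 days. (d) The safety population is 44 patients.

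**1. Nominal period lengths.** With visits at days 0, 10, 30.4, 182.6 and 365.25, the differences are 0, 10, 20.4, 152.2 and 182.65 days. In months these are 0, 0.3, 0.7, 5.0 and 6.0.

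**2. Constant rate.** Share = period length / 365.25.

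| Label | Calculation | Share |
|---|---|---|
| Discharge | 10 / 365.25 | 2.7% |
| Follow-up 1 | 20.4 / 365.25 | 5.6% |
| Follow-up 2 | 152.2 / 365.25 | 41.7% |
| Follow-up 3 | 182.65 / 365.25 | 50.0% |

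Moving discharge to day 1 or day 20 changes its share to 0.3% or 5.5% and follow-up 1 to 8.0% or 2.8%. Follow-ups 2 and 3 do not change.

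**3. Other timing patterns.** If the first-month rate is 10 times higher, the weights are 100, 204, 152.2 and 182.65 (sum 638.85). The shares become 16%, 32%, 24% and 29%, so the counts do respond to timing.

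Now suppose that, among patients who are reoperated, event times follow F(t) = 1 - exp(-t/4), t in months, cut at 12 months, where F(12) = 0.950. Follow-up 1 holds (0.221 - 0.079) / 0.950 = 15% and follow-up 2 holds (0.777 - 0.221) / 0.950 = 58%. Per month that is 0.15 / 0.67 = 0.22 against 0.58 / 5 = 0.12. Follow-up 2 has the larger count but about half the monthly share of events.

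**4. Visit windows.** The follow-up 2 period can last from 3 - 3 = 0 to 9 - 1 = 8 months. With follow-up 1 at month 1 and follow-up 2 at month 9, 3 of those 8 months (37.5%) lie beyond month 6.

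If visits are spread evenly over their windows and the rate is constant:

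- The mean follow-up 2 period is 6 - 2 = 4 months, of which 0.75 lies after month 6: 0.75 / 4 = 19%.
- The mean follow-up 3 period is 12 - 6 = 6 months, of which 0.75 lies before month 6: 0.75 / 6 = 12.5%. Stopping at month 12, where collection of reoperations ends, gives 0.75 / 5.25 = 14%.

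Spill-over across month 6 therefore runs both ways.

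**5. Can the rows be added up to the endpoint?** No. They include all reasons, and a patient with surgeries under two labels is counted in both. The overall count in SAP 24.1.1 has no time limit.

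**6. Number of events.** SAP 2.1 quotes an average of 5.9% and a range of 0.0% to 27.5% for reoperations due to ADEs/SADEs, without a time horizon. 44 x 0.059 = 2.6, and 44 x 0.275 = 12.1. If one surgery moves across month 6, the result could change from 3/44 = 6.8% (Clopper-Pearson 1.4% to 18.7%) to 2/44 = 4.5% (0.6% to 15.5%).

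**The case against.** The rows are descriptive, in a single-arm study, and the SAP claims no rate, trend or comparison between periods. The eCRF field behind the label is in a separate document, so the interval reading in steps 1 to 4 is an inference. With about 3 events, a patient listing shows timing better than any banded table, and a listing is planned. All of this stands. It keeps the point minor, although the SAP does not say that the listing will show the date or days from implant.

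A reader might infer more: that the by-visit pattern reflects the visit calendar rather than when nails fail. The documents do not support that. Step 3 shows that a strong early excess visibly changes the counts, so they mix the two influences. Nor are the rows nail failures, since they include secondary dynamization and other reasons.

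A reader might also ask for rates per patient-month. These need an end-of-observation rule for each patient. The SAP has none (section 22 describes only the reason for discontinuation), and such rates would add little with so few events.

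Lastly, some of the safety wording could be read as ending at the 6-month visit rather than at month 6. Protocol 7.2 and SAP 7 refer to time after implant. Even on the visit reading, the horizon would vary from 3 to 9 months between patients, and step 5 would still apply.

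**Conclusion.** The point holds in limited form. SAP 24.1.1 gives additional surgery no time breakdown except by visit label and has no assignment rule. If labels cover the time since the previous visit, nominal periods range from 0 days to about 6 months, and a constant rate alone puts about 92% (41.7% + 50.0%) of first-year surgeries under follow-ups 2 and 3. That part rests on the label reading and, for the two early rows, on the assumed discharge day.

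The 6-month gap does not depend on how labels are assigned. The follow-up 2 window straddles the horizon, follow-up 3 lies beyond it, the rows pool all reasons and the overall count is uncut. Neither the rows nor the overall count yields the 6-month safety result. Because few events are expected and the dates exist, this is a worthwhile tidy-up and not a threat to the study.

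**What to change.** In SAP 24.1.1, replace the five visit rows with patient counts by reoperation date minus implant date, in the same fixed periods for everyone and with a cut at 6 months (for example 0-30 days, over 30 days to 6 months, over 6 to 12 months). Make the 0-6 month count of patients reoperated because of an ADE/SADE/MDD the safety endpoint row, with its Clopper-Pearson interval. Protocol 13.1.2.2 ties the 6 months to the safety event, so state how a reoperation after month 6 for an event before it is counted.

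In the additional-surgery listing, show days from implant and the visit label, and state how the label is assigned. Rates per patient-month are optional.

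The cost is SAP wording, one date subtraction and slight extra programming. No new data are needed. A reoperation with a missing date cannot be placed in a period and should be listed as such.

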13.1.2.2 Safety Variables

The safety profile of CHIMAERA™ will be assessed through the percentage of patients that required a reoperation (i.e., additional surgery) caused by at least one of the following safety events:

- Expected or unexpected adverse effect potentially or certainly related to the CHIMAERA™ (Adverse Device Effects (ADEs)/Serious Adverse Device Effects (SADEs)) since the nail application until 6 months follow-up after nail implant.
- Medical Device Deficiency (MDDs) (i.e., breaking, loosening, or bending of the nail or of the screws) that caused an effect on the patient since the nail application until 6 months follow-up after nail implant.

All the reoperations that have occurred are considered but also those that have not occurred but that could have occurred (e.g., a patient who had a cut out but for any reasons has not been operated). It should be considered also all ADE/SADE/MDD that could have caused an additional operation.

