13.1.3.2 Evaluation of Safety

The evaluation of safety will be performed through the analysis of the secondary objective of the study: to evaluate the safety profile of the long variant of the CHIMAERA™ used in adult patients according to the manufacturer IFU in routine clinical practice from the time of surgery until 6 months follow-up after nail implant.

The safety analysis will be performed in the “safety population” which includes all patients who have undergone an intramedullary nailing technique with the CHIMAERA™ medical device.

The number and percentage of patients that required a reoperation due to at least one ADE/SADE/MDD will be calculated with a 95% confidence interval (CI). An analysis will be carried out according to degree of severity, seriousness, and relationship with the medical device.

All the reoperations that have occurred are considered but also those that have not occurred but that could have occurred (e.g., a patient who had a cut out but for any reasons has not been operated). It should be considered also all ADE/SADE/MDD that could have caused an additional operation. Therefore, the number and percentage of patients that hypothetically would have caused a reoperation due to at least one safety event will be described and calculated with a 95% CI.

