24 SECONDARY OBJECTIVES

Secondary objective: to evaluate the safety profile of the long variant of the CHIMAERA™ used in adult patients according to the manufacturer IFU in routine clinical practice from the time of surgery until 6 months follow-up after nail implant.

The safety analysis will be performed in the safety population.

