24.2 ADVERSE EVENTS

The categorical variables to be described are, N and (%) and Clopper-Pearson confidence intervals will be shown at 95.0% as well:

- Patients with at least one adverse event
- Patients with at least one serious adverse event
- Patients with at least one related adverse event (considering related as Possible, Probable and Casual relationship)
- Patients with at least one adverse event which require additional surgery

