24.3 DEVICE DEFICIENCIES (DD)

The categorical variables to be described are, N and (%) and Clopper-Pearson confidence intervals will be shown at 95.0% as well:

- Patients with at least one DD

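### No row in SAP 24.1-24.3 computes the secondary safety endpoint: the nearest rows have no 6-month limit, and they also differ from the endpoint in relatedness, in the AE/DD split and in potential reoperations

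*SAP*

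**What the plan says.** **Endpoint.** Protocol 13.1.2.2 takes the percentage of patients with a reoperation caused by an ADE/SADE or a device deficiency that affected the patient. Each type of cause is limited to the period "since the nail application until 6 months follow-up after nail implant". Reoperations that could have happened but did not are also to be considered.

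**Promised statistic.** Protocol 13.1.3.2 says "The number and percentage of patients that required a reoperation due to at least one ADE/SADE/MDD" will be given with a 95% CI. It promises a second number and percentage, also with a 95% CI, for patients with a hypothetical reoperation.

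**Collection.** Protocol 11.2 collects "ADEs/SADEs reported since the day of surgery until the last follow-up visit", sets the same period for deficiencies, and collects reoperations "performed within the 12 months after nail implant".

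**Analysis.** SAP 24 opens by restating the objective, "from the time of surgery until 6 months follow-up after nail implant", and then names the safety population. The rows that carry Clopper-Pearson intervals follow:
- SAP 24.1.1: patients with any additional surgery, with surgery because of an adverse event, and with surgery because of a device deficiency; then counts by visit, ending with "Number of patients with at least one additional surgery which occurs in follow up visit 3".
- SAP 24.2: among others, "Patients with at least one adverse event which require additional surgery", and a separate row for related events.
- SAP 24.3: "Patients with at least one DD".

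None of these rows has a date or onset condition.

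**The concern.** The study has one secondary endpoint, and the protocol gives it a time window, a causal condition and a confidence interval. The SAP should contain a row that a programmer can run to obtain that figure. If the existing rows are run as written on all collected data, they return rates over a longer window, with intervals around those rates. A reader of the report could take one of them for the 6-month endpoint.

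Collecting beyond month 6 is reasonable for a post-market study. What is missing is an instruction to cut back to month 6 at analysis, together with a row that combines the parts of the endpoint. The protocol says the study is meant to confirm the benefit/risk ratio, so the safety figure should be the one it defines.

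**Working it through.** The documents state no expected value for the safety endpoint, so there is no planned figure to reproduce. The check compares the endpoint with each candidate row and then sizes the effect of the missing time limit.

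**Step 1. Endpoint against rows.**

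| Element of the endpoint | Nearest SAP rows |
|---|---|
| Cause arises by 6 months | No time limit in any AE, DD or cause-specific surgery row |
| AE is device-related | Not required in the row for AEs requiring surgery; relatedness is a separate row |
| Related AE or deficiency, counted once per patient | AE and DD kept in separate rows |
| Deficiency affected the patient and led to reoperation | The DD row with an interval counts any deficiency |
| Potential reoperation, per patient, with CI | The could-have-led-to-surgery answers are tabulated per event, N and % only (SAP 24.2.1 on additional surgery, and 24.3.3) |

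**Step 2. Can the by-visit surgery rows stand in?** No. SAP 20 gives visit 2 a window of 3-9 months, which straddles month 6. The by-visit rows are not split by cause, and the AE and DD rows have no visit split. If 6 months is read as visit 2 itself, the overall rows still include visit 3 (window 9-15 months, SAP 21).

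**Step 3. Effect of the missing time limit.** Inputs: N = 44 (SAP 9), taking all 44 as the safety population; Clopper-Pearson 95% intervals (SAP 14). For x patients of n, the lower limit is the 0.025 quantile of Beta(x, n-x+1) and the upper limit is the 0.975 quantile of Beta(x+1, n-x).

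One extra patient adds 1/44 = 2.27 points.

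| Patients counted | Rate | 95% CI |
|---|---|---|
| 2/44 | 4.5% | 0.6-15.5 |
| 3/44 | 6.8% | 1.4-18.7 |
| 4/44 | 9.1% | 2.5-21.7 |

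Only a patient with no earlier qualifying event changes the count. A late event in a patient already counted changes nothing.

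**Step 4. How likely is such a patient?** The documents do not say. For illustration, assume that the 5.9% literature average (Protocol 6.1, SAP 2.1) is the rate over the whole collected window; the documents give no follow-up time for it, and it covers only reoperations due to ADEs/SADEs. This gives 44 x 0.059 = 2.6 patients. Let s be the assumed share of event patients whose only qualifying event is late. Then the 6-month rate is 5.9% x (1 - s), the expected number of late patients is 44 x 0.059 x s, and the chance of at least one is 1 - (1 - 0.059s)^44.

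| s | 6-month rate | Expected late patients | Chance of at least one |
|---|---|---|---|
| 0 | 5.9% | 0 | 0% |
| 0.10 | 5.3% | 0.3 | 23% |
| 0.25 | 4.4% | 0.6 | 48% |
| 0.50 | 3.0% | 1.3 | 73% |

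**The case against.** The strongest defence is that the 6-month scope is stated, in SAP 7 and at the head of SAP 24, and that Protocol 13.1 makes the SAP the technical detail of the protocol's analysis, so the definition in 13.1.2.2 still governs. On that view the limit is implicit, not absent. This has some force: a careful programmer might apply it. But the opening sentence of SAP 24 restates the objective and gives no data rule. It does not say whether the cut falls on onset or on surgery date, or at month 6 or at visit 2. Two programmers could return different rates.

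A reader might infer from the visit-3 row that the SAP plainly contradicts the 6-month limit. It does not. The limit applies to the causing event, so a reoperation at visit 3 can belong to the endpoint if its cause began by month 6. The evidence is the undated cause-specific, AE and DD rows.

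A reader might also infer that the reported safety rate will overstate harm. That follows only for the missing time limit. Including unrelated adverse events pushes a rate up as well, but splitting AE from DD and leaving potential reoperations out of the patient-level rates push the other way. The net direction is not known.

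It is also fair to say that the analysis is descriptive, with no safety threshold or test; that 2.3 points is small beside an interval about 15 points wide; and that AE start dates (Protocol 12.2) and the planned listings would probably allow a 6-month count of adverse events by hand. These points limit the consequence. They do not supply the percentage and interval that Protocol 13.1.3.2 promises.

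**Conclusion.** The point holds: SAP 24.1-24.3 has no row for the secondary endpoint. The nearest rows lack the 6-month limit and also depart from the definition in relatedness, in the AE/DD split and in potential reoperations. A date filter alone would therefore not produce the endpoint.

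With 44 patients in the safety population, the missing limit is worth 2.3 points for each patient whose only qualifying event began after month 6, and about 3 points on the upper confidence limit (15.5 to 18.7 in the example). The number of such patients is unknown and may be zero; the 23-73% chances for late shares of 10-50% illustrate assumptions and are not evidence about this device. The other departures cannot be sized from the documents.

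The documents do not support shortening data collection. Gathering events past month 6 does no harm to a 6-month endpoint that is cut correctly at analysis. The SAP should be corrected before the analysis is run, but nothing here undermines the study's conduct.

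**What to change.** Add patient-level endpoint rows to SAP 24, each with N, % and a Clopper-Pearson 95% interval. Count patients with at least one related adverse event (possible, probable or causal), or a deficiency that affected the patient, with onset by 6 months after implant, that:
- (a) required additional surgery;
- (b) required, or could have led to, additional surgery.

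State three rules with these rows:
1. Whether the limit is 6 months by date, using the AE start date and a deficiency date if there is one, or the date of visit 2. If visit 2 is chosen, say how patients without that visit are handled.
2. That the limit applies to the onset of the causing event, not to the reoperation date, so a reoperation in months 6-12 still counts if its cause began in time.
3. That events with later onset are reported in a separate row, so that no information is lost.

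Keep the existing rows as supporting description and leave the collection period unchanged.

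The cost is minor programming. AE start dates, relatedness and the answers on required or potential surgery are already planned. The documents name no deficiency date, so one eCRF field may be needed. The headline row may contain slightly fewer events. No new patients or charts are required.
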